2.2. Endpoints

2.2.1. Primary Endpoints

- Incidence and severity of AEs, and SAEs
- Absolute changes and changes from baseline in clinical laboratory parameters (hematology, blood chemistry and urine values), including assessment of shifts from baseline to abnormal values
- Absolute changes and changes from baseline in vital signs & ECG parameters

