7.1.1. Adverse Events

An AE is defined as any untoward medical occurrence in the form of signs, symptoms, abnormal laboratory findings, or diseases that emerges or worsens relative to baseline during a clinical study with an investigational product, regardless of causal relationship and even if no investigational product has been administered.

In this study, the term "investigational product" refers to the radiolabeled imaging final product ⁶⁸Ga-PSMA-R2.

Unchanged/stable pre-existing, chronic medical conditions present at baseline, or those medical conditions related to the underlying disease should not be recorded on AE pages of the eCRF. However, in case of worsening of a pre-existing condition, this should be considered and reported as AEs.

- Relationship to IP,
 - based on temporal association: temporal relationship between administration of the IP and AEs occurrence is compatible,
 - based on AEs presentation and IP characteristics
 - If no alternative explanations (patient's medical history, patient's concomitant treatment, circumstance of AEs occurrence) are identified

- Not related to IP:
 - In case an alternative explanation regarding the AEs occurrence had been identified.

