8.2.1. Safety and Tolerability Analyses

Safety evaluations on the full analysis set will be based on the incidence, type, severity and consequences (e.g. study discontinuation) of an AE as well as on clinically significant changes in the patient's ECGs, vital signs, and clinical laboratory results. ECG parameters will include heart rate (HR), RR interval, PR interval, QRS width and QTc interval. Statistical analysis includes descriptive tabulation using measures which are absolute and relative frequencies for categorical data and means, standard deviations, medians and interquartile ranges for continuous data for observed values as well as for changes from baseline in continuous parameters at each measuring time. Clinical laboratory data, ECGs and vital signs will also be presented graphically in terms of box plots of absolute values over time and changes from baseline over time. Clinical laboratory data with respect to the normal ranges of values provided by the laboratory and with respect to pre-defined levels of change in these values.

All original AE/SAE terms will be coded using the current Medical Dictionary for Regulatory Activities (MedDRA) version. All Adverse events will be listed on an individual basis. AEs will be summarized by System organ classes and preferred terms on a patient basis. Patients with more than one adverse event within a particular SOC and PT will be counted only once for that SOC and PT. The type and incidence of AEs/SAEs, as well as severity and causality will be tabulated on a patient basis using the worst severity/causality for patients with several AES within the same particular SOC and PT.

Only treatment emergent events will be included in summaries of AEs, but all adverse events will be presented in listings. Summaries of adverse drug reactions will also be produced, which are defined as treatment emergent adverse events at least possibly related to treatment.

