14.1.1.2. Relationship to Study Medication

A related TEAE is defined as a TEAE with a relationship to study medication as "Reasonable possibility" according to the investigator. TEAEs with a missing relationship to study medication will be regarded as related to study medication. If a patient reports the same AE more than once within that SOC/ PT, the AE with the worst-case relationship to study medication will be used in the corresponding relationship summaries.

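### Protocol 7.1.1 calls an event unrelated once any other explanation is found; this is narrower than the relatedness the analysis counts and, applied as written, can only lower the related-event summaries.

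*Protocol*

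**What the plan says.** **Site rule.** Protocol 7.1.1 has two classes. Under relationship to the product it lists compatible timing, the event's presentation together with the product's characteristics, and a third element: "If no alternative explanations (patient's medical history, patient's concomitant treatment, circumstance of AEs occurrence) are identified". The not-related class has a single criterion: "In case an alternative explanation regarding the AEs occurrence had been identified".

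**Instruction to sites.** Protocol 7.6.2 directs investigators to apply the adverse event definitions of the preceding sections when they fill in the eCRF adverse event pages.

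**Protocol analysis.** Section 8.2.1 states: "Summaries of adverse drug reactions will also be produced, which are defined as treatment emergent adverse events at least possibly related to treatment".

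**SAP analysis.** SAP 14.1.1.2 reads "A related TEAE is defined as a TEAE with a relationship to study medication as" Reasonable possibility, in the investigator's judgment. It adds two conservative rules: "TEAEs with a missing relationship to study medication will be regarded as related to study medication", and, for repeated events within a SOC and PT, "the AE with the worst-case relationship to study medication will be used in the corresponding relationship summaries".

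**Late reporting.** Protocol 7.1 and 7.7 limit SAE reporting after follow-up to events possibly related to the product or the study procedures. Section 7.7 applies the same limit to screen failures from the date of failure.

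**The concern.** Take an event with compatible timing, a plausible product role and a plausible competing cause, such as a concomitant drug. Protocol 7.1.1 makes it not related. In ordinary usage, both a possible relationship and a reasonable possibility would admit it. One analysis variable therefore has three wordings, and the one addressed to the person who codes the event is the narrowest.

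The trial has no control arm and so no concurrent background rate. Investigator causality is one of the few means of separating product effects from background illness. A rule that errs in one direction makes the related-event tables look cleaner than the investigators' own view of what is possible. The same judgment decides whether an SAE arising after follow-up is reported at all.

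**Working it through.** The documents give no figure for relatedness or for related-event rates, so there is nothing to reproduce. The check compares the texts and then gives a labelled illustration.

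**1. The same event under each text**

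| Event with compatible timing | Protocol 7.1.1 | Protocol 8.2.1 | SAP 14.1.1.2 |
|---|---|---|---|
| No alternative found, presentation fits | Related | Counted | Counted |
| Alternative found, product role still possible | Not related | Counted, if possible keeps its usual meaning | Counted, if the investigator sees a reasonable possibility |
| Alternative found, no plausible product role | Not related | Not counted | Not counted |
| Relationship left blank | No rule | No rule | Counted |

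Only the second row conflicts, and it moves in one direction: 7.1.1 takes events out of the related class and puts none in.

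**2. Does the site rule reach the analysed variable?** The SAP takes the investigator's category as given. Section 7.6.2 sends the investigator to the protocol's definitions, and 7.1.1 holds the only relatedness criteria in the protocol text available. Following the plan therefore carries the narrow rule into the SAP count.

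**3. Do the SAP's conservative rules repair it?** The missing-as-related rule acts on blanks, not on events actively coded not related. The worst-case rule helps only when another event in the same SOC and PT was coded related. Neither recovers an event whose only coding is not related.

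**4. Outputs touched**
- Affected: TEAEs by relationship (SAP 14.1.1), the adverse drug reaction summaries (protocol 8.2.1), and possibly late SAE reporting (protocol 7.1, 7.7).
- Not affected: overall AE and SAE incidence and severity, the individual listings of all events, and SAE reporting up to the last follow-up visit, which protocol 7.6.3 requires whatever the relationship.

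**5. Scale (illustration only).** With the planned 30 patients, one reclassified patient is 1/30 = 3.3 percentage points. In the SAP's population columns it is 1/12 = 8.3 points for mPCa and 1/(6 + 12) = 5.6 points for PCa-BR.

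The next table rests on assumptions that are not in the documents. Let p be the share of 30 patients with an at least possibly related event. Let q be the share of those who drop out of the related class because an alternative was identified.

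- Expected related patients = 30 × p × (1 − q)
- Chance of at least one = 1 − (1 − p(1 − q))^30

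| p | q = 0 | q = 25% | q = 50% | q = 75% |
|---|---|---|---|---|
| 10% | 3.0; 95.8% | 2.25; 90.4% | 1.5; 78.5% | 0.75; 53.2% |
| 20% | 6.0; 99.9% | 4.5; 99.2% | 3.0; 95.8% | 1.5; 78.5% |
| 30% | 9.0; >99.9% | 6.75; >99.9% | 4.5; 99.2% | 2.25; 90.4% |

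For example, with p = 10% and q = 50%: 30 × 0.10 × 0.50 = 1.5, and 1 − 0.95^30 = 78.5%. With q = 0 nothing is lost.

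**The case against.** The strongest reply is that the SAP counts a category, not the bullets of 7.1.1. An investigator may choose Reasonable possibility on its plain meaning, and the eCRF and its completion instructions are not among the documents. A reader might infer that related events are in fact under-counted. The documents do not show that; it depends on sites applying 7.1.1 as written. This stands, and the point is conditional for that reason. Section 7.6.2 nevertheless tells sites to do exactly that.

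A reader might also infer that the primary safety result is pushed toward zero. It is not. The primary endpoint is "Incidence and severity of AEs, and SAEs", with no causality filter, and SAP section 14 repeats it without one. The study is descriptive, and no decision rule is tied to a related-event rate. Nor do the documents support a claim that these patients nearly always have an alternative explanation. No rate is given, and 7.1.1 itself keeps stable pre-existing and disease-related conditions off the adverse event pages unless they worsen.

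Other passages are softer. Section 7.6.2 asks for other causality factors beside causality, and 7.6.3 asks for the possible causes of an SAE in the plural. The related bullets in 7.1.1 are not joined by an explicit conjunction, and neither 8.2.1 nor the SAP says how to class an event with a competing cause. These points show an intention to allow several causes. They do not change the not-related line, which stands alone and is met by any identified alternative.

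**Conclusion.** The point holds as an inconsistency with a known direction and an unknown size. If sites apply 7.1.1 as written, the related-TEAE and adverse drug reaction summaries can only fall, and fewer SAEs may qualify as possibly related after follow-up. This rests on two assumptions: that investigators follow 7.6.2 when they choose the eCRF category, and that possible relationship keeps its ordinary meaning, under which a competing cause does not exclude the product. The size cannot be found from the documents, and the scale figures above are not estimates. Because the rule is stated rather than merely missing, and rewording it is cheap, it should be changed.

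**What to change.** Replace the 7.1.1 criteria with the category the SAP already analyses:

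- **Related:** a reasonable possibility that the product caused or contributed to the event, even if another explanation exists.
- **Not related:** no reasonable possibility that it did.

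Use this definition for adverse drug reactions in protocol 8.2.1 and for possibly related in 7.1 and 7.7. Timing, presentation and competing causes can remain as factors to weigh, but an alternative explanation should no longer settle the matter alone. SAP 14.1.1.2, including its missing-data and worst-case rules, can stay as it is.

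The cost is a protocol wording change, with no new data, visits or patients. The downside is that slightly more events will be classed as related.

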7.2. Abnormal Laboratory Findings and Other Objective Measurements

All clinically relevant abnormal laboratory findings must be captured and reported as AEs. Abnormal laboratory findings and other objective measurements that meet the criteria for SAE, result in discontinuation of the Investigational Product, or require medical intervention, should be captured and reported on the SAE/AE pages of the eCRF.

If reporting an abnormal laboratory finding on the AE pages of the eCRF, a clinical description or diagnosis should be recorded rather than the abnormal value itself, if this is available (for example "anemia" rather than "decreased red blood cell count" or "hemoglobin = 10.5 g/dL").

In the event of unexplained clinically abnormal laboratory values, the tests should be repeated immediately and followed up until returns to normal range and/or an adequate explanation of the abnormality is found. If a clear explanation is established, this must be recorded on the eCRF.

7.3. Baseline Medical Conditions

Medical conditions present at the screening visit, that do not worsen in severity or frequency during the study are defined as Baseline Medical Conditions and are not adverse events. These medical conditions should be adequately documented on the appropriate page of the eCRF, i.e. medical history page.

However, worsening of medical conditions present at the initial study visit, either severity or frequency during the study should be recorded and reported as AEs.

7.4. Baseline Medications

Any medication taken prior to investigational product administration will be considered baseline medications. Any medications taken from the Day of administration (Day 1) to the end of the trial will be considered concomitant medications and captured on the appropriate eCRF page.

7.5. Clinical Condition Impairment

Exacerbation or worsening of symptoms will be recorded on the AE page of the eCRF.

7.6. Procedures for Obtaining, Recording and Reporting Adverse Events

7.6.1. Obtaining Adverse Events

Adverse event data will be obtained by the Investigator at scheduled study visits, based on information spontaneously provided by the patient and/or through questioning. The patient will be instructed upon signing the ICF to contact the Investigator if any adverse or unusual event occurs during his participation in the study.

To obtain adverse events, simple questions with minimal connotations should be used as the initial questions at all evaluation points during the study. For example:

- How did you feel since your last visit?
- Have you had any health problems since you were visited?

In the case that a patient was seen by a different health care professional (e.g. at a different institution), in relation with an adverse event, every effort should be made by the Investigator to contact the treating physician in a timely manner to obtain all necessary information and report the event appropriately in the eCRF.

7.6.2. Recording of Adverse Events in the eCRF

Adverse events will be recorded in the patient's medical records (source document) and eCRF, whether observed by the Investigator, the investigational staff, or spontaneously reported by the patient.

As quality and precision of acquired AE data is of key importance, Investigators should use the adverse event definitions provided in the sections above and observe the following guidelines when completing the AE pages of the eCRF:

- Whenever possible, recognized medical terms should be used to describe AEs rather than colloquialisms (e.g. 'influenza' rather than 'flu'), and abbreviations should be avoided.
- Adverse events should be described using a specific clinical descriptions or diagnosis rather than component signs or symptoms (e.g. 'congestive heart failure' rather than 'dyspnea, rales and cyanosis'). However, signs and symptoms that are considered unrelated to an identified disease or syndrome might be reported as individual AEs on the eCRF if no clearer diagnosis can be drawn.
- Adverse events occurring secondary to other events (e.g. sequelae or complications) should be identified by the primary cause. A primary AE, if clearly identifiable, generally represents the most accurate clinical term to record on AE pages of the eCRF.

It is important that each AE report includes a description of the event, seriousness status and criteria, duration, severity, and causality, other causality factors (if any), any concomitant medications dispensed, concomitant procedure prescribed or other action taken, including dose modification and/or discontinuation of the investigational product and its outcome as per the end of the reporting period.

7.6.3. Serious Adverse Events Requiring Expedited Reporting

Any SAE requires expedited reporting to the Sponsor or designee, regardless of relationship to the Investigational Product.

An SAE is defined as an AE that at any dose:

• **Resulted in death**: i.e. the AE causes or contributes to the death.

- **Was life threatening**: i.e. the AE places the patient at immediate risk of death; the definition does not apply to an AE that hypothetically might cause death if it was more severe.
- **Required or prolonged hospitalization**: i.e. the AE requires at least a 24-hour in-patient hospitalization or prolongs a hospitalization beyond the expected length of stay. Hospital admissions for surgery planned before trial entry, for social reasons or for normal disease management (including treatment adjustment) are not to be considered as SAE according to this criterion.
- Is a congenital anomaly or birth defect: i.e. an adverse outcome in a child or fetus of a patient's partner exposed to the investigational product, before conception or during pregnancy.
- **Resulted in persistent or significant disability or incapacity**: i.e. the AE resulted in a substantial disruption of the patient's ability to conduct normal life functions.
- Was a medically important condition: Such an event may not be immediately lifethreatening or result in death or hospitalization but may jeopardize the patient or may require intervention to prevent one of the other outcomes listed in the above definition should also usually be considered as serious.

Investigators must indicate the possible cause(s) of the SAE in the appropriate section of the SAE reporting form (e.g. underlying disease, study treatment, other treatment[s], study procedures, or other cause[s]).

7.6.4. Pregnancy

The occurrence of a pregnancy of a partner of a trial patient discovered within 1 week after last administration of the IP and up to the end of follow-up period, is to be communicated to the Sponsor in an expedited manner with the same procedure and timelines as for SAEs (see paragraph 7.6.5), independently from the occurrence of an AE.

7.6.5. Expedited Reporting Procedure

Besides AEs and SAEs entry in the eCRF, investigators must notify the Sponsor or designee **within 24 hours** of awareness of a new SAE/pregnancy case or of new information on a previously reported SAE/pregnancy case (follow-up), regardless of relationship to the investigational product.

The Investigator/Reporter must complete an SAE form and the following minimum information is required as initial notification:

- Clear identification of the Investigator/Reporter with full contact information,
- A unique clinical trial identification
- Patient identification details (trial number, site number, identification code number, date of birth),
- Investigational Product administration details (product name, dose and dates),

- Reported event as a diagnosis term with its description (or a brief description of signs/symptoms/clinical course if the diagnosis is not available)
- Date of onset of the event,
- Reason(s) for considering the event serious,
- Investigator causality assessment

The opinion of the Investigator about the causal relationship between the event and the IP is required. Even if not all the facts are known, an initial report should be sent to the Sponsor.

The initial report must be followed by a detailed report as soon as possible.

Any additional information received on an initial SAE report must be sent to the Sponsor following the same timelines.

If considered necessary by the Sponsor and in order to allow a sound medical assessment of the reported SAEs, the Sponsor may request additional documentation such as technical investigation reports, histology findings, hospital discharge documents. All these additional documents must be blinded with respect to the patient's name and provided to the Sponsor in due time by email ([contact]).

When the Investigator determines that no additional information is likely to be available, a final report should be provided.

7.6.6. Reporting to the Competent Authorities and IRB/IEC

The Sponsor or designee will assume responsibility for appropriate reporting of Suspected Unexpected Serious Adverse Reaction (SUSAR) to the Competent Authorities and Independent Ethics Committee(s)/Institutional Review Board(s) (IEC/IRB) according to local laws and regulations.

The Sponsor will inform Competent Authorities, IRB/IEC, and Investigators of "findings that could adversely affect the safety of patient and impact the conduct of the study or alter the IRB/IEC's approval/favorable opinion to continue the study".

Copies of safety reports should be kept in the Investigator file as well as inserted into the relevant Investigator Brochure. In addition, all correspondence relating to their notification to the Competent Authorities and IRB/IEC should be maintained in the Investigator file.

Development safety update report (DSUR)/IND report will be sent to inform competent authorities, IRB/IEC, and Investigators.

7.7. Reporting Period

Adverse Events are collected on an ongoing basis from signing of Informed Consent until the last follow up visit.

All SAEs, including deaths, independently of causality, that occur from informed consent until the last scheduled follow-up visit will be recorded on an SAE form, in addition to the eCRF data entry. After the last follow-up visit, the Investigator must report to the Sponsor only SAEs possibly related to ⁶⁸Ga-PSMA-R2 or to the study procedures.

All SAEs must be followed-up by the Investigator until resolution or stabilization, and follow-up information must be reported to the Sponsor according to the reporting procedure.

All pregnancy cases occurring one week after IP administration and until the last follow-up (Day 28) will be reported according to the SAE reporting procedures. All pregnancy reports will be followed-up until delivery.

A last batch of queries will be sent after Last Patient Last Visit for all AEs with ongoing/unknown outcomes. After the last batch of queries with all collected data have been fully processed, eCRFs and database will no longer be updated. Only SAEs and medically relevant ongoing/unknown outcome AEs will be followed-up until resolution or stabilization. Beyond this defined reporting period, any new unsolicited serious AE spontaneously reported to CRO/Sponsor by the Investigator would however be collected and processed by pharmacovigilance.

Any patient who received a partial or full dose of the investigational product and who withdraws prematurely or is withdrawn by the Investigator from the trial, should have a follow-up safety visit 28 (\pm 3) Days after the investigational product administration.

If a patient is documented as lost-to follow-up or consent withdrawal, ongoing/unknown outcome AEs will not be followed-up.

For screen failure patients, new AEs and updates must be recorded in eCRFs until the date the patient was determined to be a screen failure. Beyond that date, only SAEs possibly related to the investigational product or to the study procedures will be reported to the CRO/Sponsor.

